15.3.2 Interim analysis

There will be no interim analysis.

15.3.3 Secondary endpoint analysis

Efficacy endpoints

All efficacy secondary endpoints will be analyzed in the ITT and PP populations.

Progression-free survival (PFS) will be analyzed as a secondary criterion of efficacy. PFS will be defined as the time from date of randomization and resistant disease or relapse or death from any cause. Any patient not known to have died at the time of analysis will be censored based on the last recorded date on which the patient was known to be alive (i.e. their status must be known at the censored date and should not be lost to follow up or unknown). PFS will be analyzed at the time of final analysis using a stratified log-rank test (stratification factor, PS). A Cox model will also be used to test the effect of treatment and will include terms for prognostic factors (PS, age and cytogenetic group).

The analysis of objective response rate (i.e. CR or PR) will be performed using logistic regression including treatment factor and PS. Secondary analysis will be performed where the logistic regression model will allow for the effect of treatment, and will also include prognostic factors as for OS and PFS. Percentage of patients with CR, CRi, CRp and PR will be calculated and associated exact 95% CIs will be presented by treatment group. Median duration of response from onset of response (RFS) will be calculated and summarized by treatment group for the subset of responders.

Absolute and relative change from baseline EORTC quality of life (QoL) questionnaire scores will be described in each treatment group. EORTC QoL questionnaire scores will be compared across time in each treatment group using a mixed model for repeated data.

Time until QoL deterioration will be defined as a decrease in QoL score from baseline without any return to a better state during the study. A threshold of 10% decrease in QoL score will be primarily used. Other thresholds may be used as exploratory analyses. Death will also be considered as a QoL deterioration. Time to QoL deterioration will be summarized using Kaplan-Meier methods and will be compared between treatment groups using a stratified log-rank test (stratification factor, PS).

Percentage of patients who need transfusions (red blood cells and/or platelets), mean number of transfusions by patient and mean number of hospitalizations (more than over 24 hours) required during the study will be described with their corresponding 95% CI in each treatment group.

The primary analysis of the main secondary endpoints for efficacy will take place once all patients have completed 12 months in the study as for the primary endpoint. A further supportive set of analyses will take place following completion of 24 months in the study for all patients.

Safety endpoints

All subjects who received at least one dose of investigational products will be included in the safety analyses. Safety data will be summarized using actual treatment received, regardless of randomized treatment.

Safety and tolerability will be assessed in terms of AEs, SAEs, laboratory data and vital signs which will be collected for all subjects. AEs will be coded according to the Medical dictionary for regulatory activities (MedDRA) version 15.1 or higher. The intensity of AEs will be graded according to the NCI-CTCAE (version 4.0).

AEs, AE leading to study treatment discontinuation, AE related to study treatment, and SAEs will be listed individually by subject, and summarized by System Organ Class (SOC) and Preferred Term (PT) by treatment group. Summary of AEs with NCI-CTCAE grade 3 or 4 and most frequent PT will also be provided.

Specific attention will be given to NCI-CTCAE Grade 3 or 4 of pancreatic toxicity, Grade 3 or 4 of hepatotoxicity, allergic reactions or coagulation disorders, known to be potentially related to L-asparaginase as well as to hypoproteinemia and hyperglycemia/diabetes events.

Vital signs and laboratory data will be listed and summarized by actual treatment group based on the safety analysis set. Summary of absolute values over time (one table per vital sign/laboratory parameter) and summary of change from baseline values over time (one table per vital sign/laboratory parameter) will be presented. Patients with vital sign/laboratory values of NCI-CTCAE grade 3 or 4 will be identified.

Pharmacokinetics and immunogenicity will only be assessed on the subgroup of subjects having received GRASPA. Samples for amino acids (asparagine, aspartate, glutamine, and glutamate), and whole blood asparaginase will be taken on Days 11, 13, 18 and 27 of the first two cycles of treatment after amendment implementation. Summary of absolute values over time (one table per parameter) and summary of change from baseline values over time (one table per parameter) and summary of change from baseline values over time (one table per parameter) and summary of change from baseline values over time (one table per parameter) will be presented separately for patients recruited before and after the protocol amendment. Whole blood L-asparaginase concentrations from this study will be evaluated using a population pharmacokinetic analysis. Prior to the analysis, the concentration data will be combined with concentration data collected in previous clinical studies. The model building will be conducted using NONMEM (Icon Development Solutions, [name], USA, 2009) and reported separately.

16. Ethics and regulatory

The Sponsor and investigators must ensure that the study will be carried out in compliance with the protocol, the principles of ICH GCP and the declaration of Helsinki (appendix 9)

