8.5.4 Dosage modifications for GRASPA

- If patient cannot receive GRASPA, for another reason than an adverse event, treatment may be postponed no later than one week after the initial scheduled day. A minimum two weeks interval between GRASPA infusions must be insured.
- In case of allergic reaction during administration, stop the administration immediately and then to administer the necessary symptomatic treatments, according to standard of care. Further administration of GRASPA will be at investigator judgment, considering possibility of premedication anticipated for such case.
- In case of any Grade 3 or 4 adverse event related to GRASPA occurring in two successive infusions, GRASPA should be discontinued.
- In the event of bilirubin levels >3 times upper limit of normal or transaminase levels >10 times upper limit of normal, treatment with GRASPA should be discontinued.

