5.7. Pharmacokinetic Evaluations

Pharmacokinetic, pharmacodynamic and immunogenicity parameters will only be assessed on the subgroup of subjects having received GRASPA. Samples of amino acids (asparagine, aspartate, glutamine and glutamate) and whole blood asparaginase will be taken on Days 11 and 18 of the first two cycles for all patients, on Days 11 and 18 of the remaining cycles for patients included before protocol amendment and on Days 11, 13, 18 and 27 of the first two cycles for patients included after the protocol amendment. Summary of absolute values over time and summary of change from baseline values over time will be presented separately for patients recruited before and after the protocol amendment. Prior to analysis, the concentration data will be combined with concentration data collected in previous clinical studies. The model building will be conducted using NONMEM (Icon Development Solutions, [name], USA, 2009) and reported separately.

Regarding PK/PD analyses, as only 2 measurements of total blood asparaginase will be performed (D11 - 5 minutes before administration and D18), no accurate pharmacokinetic curve will be available for encapsulated asparaginase. Only those pharmacokinetic measurements which can be calculate using two timepoints will be presented.

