5.8.2.2. Amino-acids and total blood asparaginase

This procedure is applicable to patients under GRASPA® treatment only.

Amino acids will be described at D11 and D18 of the first two cycles of chemotherapy on all patients, at D11 and D18 of every remaining cycle for patients included before the protocol amendment and at D13 and D27 of the first two cycles for patients included after the protocol amendment:

- asparagine
- aspartate
- glutamine
- glutamate

Total blood asparaginase will be described at D11 and D18 of the first two cycles of chemotherapy on all patients, at D11 and D18 of every remaining cycle for patients included before the protocol amendment and at D13 and D27 of the first two cycles for patients included after the protocol amendment:

- Plasmatic asparaginase
- Total asparaginase
- Encapsulated asparaginase
- Free asparaginase

Encapsulated asparaginase is defined as: $\text{Total asparaginase} - \text{Plasmatic asparaginase}$.

Free asparaginase is defined as: $\text{Plasmatic asparaginase} / \text{Total asparaginase}$

For lab values reported in the format BLLQ (Below Lower Limit of Quantification), the value of limitation should be used for the purpose of including this data in the calculation of summary statistics:

Parameters	Lower limit of quantification
Asparagine	0.519 µmol/L*
Aspartate	0.987 µmol/L*
Glutamine	49.802 µmol/L*
Glutamate	10.716 µmol/L*
Plasmatic asparaginase	2.5 U/L*
Total asparaginase	75 U/L *

* These data will depend of the central laboratory, and will be confirmed before analyses.

Raw results as well as absolute and relative change from D11 will be described at each time point between treatment groups, and presented separately for patients recruited before and after the protocol amendment.

Absolute change in biological parameter between D18 and D11 will be calculated according to the formula: *Biological parameter at D18 – Biological parameter at D11*

Relative change in biological parameter between D18 and D11 will be calculated according to the formula:

$$\frac{\text{Biological parameter at D18} - \text{Biological parameter at D11}}{\text{Biological parameter at D11}} \times 100$$

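### SAP 5.8.2.2 takes PK/PD change from an unspecified Day 11, where the protocol and SAP 5.7 plan change from baseline; on a same-course reading, sustained asparagine depletion is tabulated as no change

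*Protocol*

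**What the plan says.** Protocol 15.3.3 plans tables of absolute values and of change for the amino acids and whole blood asparaginase: "summary of change from baseline values over time (one table per parameter) will be presented separately" for patients recruited before and after the amendment. SAP 5.7 says the same: "Summary of absolute values over time and summary of change from baseline values over time will be presented separately". Neither section says which sample is the baseline.

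SAP 5.8.2.2 covers the same measurements but sets a different reference: "Raw results as well as absolute and relative change from D11 will be described at each time point between treatment groups". Its formula sentence reads "Absolute change in biological parameter between D18 and D11 will be calculated according to the formula", followed by D18 minus D11, and by the same difference divided by D11 for relative change. There is no course index and no formula for D13 or D27.

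The sampling is repeated. D11 and D18 are taken in the first two cycles for everyone on GRASPA, and also "at D11 and D18 of every remaining cycle for patients included before the protocol amendment". SAP 5.7 describes the two-sample schedule as "D11 - 5 minutes before administration and D18", so that D11 value is pre-infusion. Patients included after the amendment have several D11 samples: protocol Table 5 lists one before the infusion and others from 5 minutes to 6 hours after it ends.

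GRASPA is given on Day 11 of each 28-day course (protocol 8.4 and 9.2).

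**The concern.** A pre-infusion D11 value is a pre-GRASPA value in course 1 only. From course 2 on it is a trough after the previous infusion. If D18 is compared with the D11 of the same course, the table shows what the latest infusion added, not how far the patient is from the untreated state. For asparagine, where the wanted effect is a low value, the patient with the most sustained depletion then gets the smallest reported change.

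The course 1 sample matters because PK/PD is measured only in the GRASPA arm (protocol 8.7.2), so no control series can supply an untreated level.

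The SAP uses visit minus baseline for routine laboratory tests (5.8.2.1) and vital signs (5.8.3). Section 2 says the SAP will outline differences from the protocol's planned analysis, but section 6 does not list this one.

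**Working it through.** The plan states no figure that depends on this definition, so there is nothing to reproduce. The check applies the SAP's formulas under each possible reference.

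**Inputs**
- Asparagine quantification limit 0.519 µmol/L and total asparaginase limit 75 U/L; values below the limit are set to it (SAP 5.8.2.2, limits still to be confirmed).
- Asparagine before GRASPA: not in the documents. Assumed 20, 50 or 80 µmol/L.
- Duration of asparaginase activity above 100 IU/L in the earlier randomised ALL trial: mean 20.5, SD 5.2 days (protocol 3.4).

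**Asparagine, course 2, D18 at the limit (0.519)**

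Absolute change = D18 - reference. Relative change = 100 × (D18 - reference) / reference.

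| Course 1 D11 (assumed) | Course 2 D11 | Change from course 2 D11 | Change from course 1 D11 |
|---|---|---|---|
| 20 | 0.519 (still depleted) | 0 (0%) | -19.5 (-97.4%) |
| 20 | 2 (10% of start) | -1.5 (-74.0%) | -19.5 (-97.4%) |
| 20 | 10 (50% of start) | -9.5 (-94.8%) | -19.5 (-97.4%) |
| 50 | 0.519 | 0 (0%) | -49.5 (-99.0%) |
| 50 | 5 | -4.5 (-89.6%) | -49.5 (-99.0%) |
| 50 | 25 | -24.5 (-97.9%) | -49.5 (-99.0%) |
| 80 | 0.519 | 0 (0%) | -79.5 (-99.4%) |
| 80 | 8 | -7.5 (-93.5%) | -79.5 (-99.4%) |
| 80 | 40 | -39.5 (-98.7%) | -79.5 (-99.4%) |

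A patient still at the limit scores exactly zero. After recovery to half the starting level, the absolute change is about halved but the relative change hardly moves. The relative change falls clearly only when D11 is still close to the limit.

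**Asparaginase, course 2**

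Illustration: activity t days after one infusion is A(t) = 100 × 2^((20.5 - t)/h), with assumed half-life h from 5 to 30 days. Then D11 = A(28) and D18 = A(7) + A(35), with the 75 U/L floor applied.
- h = 5: D11 35, set to 75; D18 663. The change is +588 U/L (+784%) from either reference.
- h = 30: D11 84; D18 208. The change is +124 U/L (+148%) from same-course D11, against +133 U/L (+178%) from course 1 D11 set to 75.

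The rise shrinks somewhat at long half-lives. It does not vanish.

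**How often could D11 still be depleted?**

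The documents do not say. As a rough guide, a normal distribution with mean 20.5 and SD 5.2 puts 2.2% of durations beyond 31 days, 7.5% beyond 28 and 19.3% beyond 25 (28 days with the 3-day course window). Suppose those shares p were still depleted, everyone else had recovered fully, and the start was 50 µmol/L. The mean relative change would be (1 - p) × (-99.0%): about -97%, -92% and -80%. This carries an activity threshold in ALL over to asparagine in AML, and the protocol's summary of that trial states neither its dose nor its number of infusions.

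**The case against.** Several stronger readings are tempting, and the documents do not support them.

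- *The SAP has replaced baseline by same-course D11.* That is the natural reading of 5.8.2.2, but no course is named and 5.7 still says baseline. What is on the page is an inconsistency with an undefined term.
- *Sustained depletion would be reported as no effect.* This is true of the change table alone. Raw results at each time point are planned in the same sentence, SAP 8.1 lists summary statistics over time (14.2.9.1), and Table 14.2.9.2 counts patients with asparagine depletion. SAP 5.2.1 also reports medians, which a small depleted share would barely move.
- *Asparaginase is equally affected.* It is not: D18 follows a fresh infusion, and the change stayed clearly positive in every case tried.
- *Carry-over is common.* The only asparagine duration given is depletion sustained over 7 days in the elderly ALL study (protocol synopsis). The rule "A minimum two weeks interval between GRASPA infusions must be insured" in protocol 8.5.4 sets a floor and is not the schedule, so it does not make a 14-day trough typical.
- *The amendment contaminates the newer data.* The SAP splits patients by when they were included. Those included afterwards have a GRASPA-free D11 in course 1, and those already on treatment are shown separately.

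Change over one infusion is also a legitimate measure, because it shows whether each dose still acts. That point stands and is a reason to keep it under its own label. It does not reconcile 5.8.2.2 with 5.7 and the protocol.

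**Conclusion.** The point holds as a conflict of definitions with a predictable consequence. On the natural same-course reading, a later-course patient with asparagine below the limit at both D11 and D18 is tabulated at 0%, against -97% to -99% from the course 1 pre-infusion value. The zero follows from the SAP's own substitution rule. The comparison figure rests on an assumed starting level of 20 to 80 µmol/L. The number of patients concerned cannot be derived from the documents.

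A reader might infer that the PK/PD objective itself is compromised. The documents do not support that: the affected outputs are descriptive change tables in one arm, and the other planned outputs would still show depletion. The overall survival analysis, the sample size and the 0.80 hazard-ratio criterion are unaffected.

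**What to change.** Before database lock, in SAP 5.7 and 5.8.2.2:

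1. Define the PK/PD baseline as the course 1 Day 11 pre-infusion sample, the last value before any GRASPA.
2. Compute change at D13, D18 and D27 in all sampled courses from that value, with formulas for each day.
3. Keep D18 minus same-course pre-infusion D11 as a secondary column labelled *change over this infusion*.
4. Define depletion for Table 14.2.9.2, which the SAP text leaves open.

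The cost is a few sentences and a programming change. The course 1 Day 11 sample is already scheduled for every GRASPA patient. Patients who lack it drop out of the baseline-change column but stay in the raw-value tables.

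Separately, protocol 8.5.3 refers to a 14-day GRASPA interval when cytarabine is stopped, while 9.2 gives one infusion per 28-day course. These passages must be reconciled, because the interval determines what a later Day 11 value represents.

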16.1 Independent Ethics committees and regulatory authorities submissions

The Sponsor must submit the protocol and appropriate related materials to Ethic Committee(s) and local Competent Authority according to national legislation. Approval from Ethic committee(s) and competent authorities must be granted prior to the study start.

Any substantial amendment to the protocols will be implemented only after approval of these bodies as well.

Regulatory Authorities will be provided with amendments if any, reports on SAEs, and the Integrated Clinical Trial Report according to national regulations.

16.2 Informed Consent Form of trial subjects

Prior to any trial related activity, the Investigator must give the subject (and/or parents or the subject's legally acceptable representative, if applicable) oral and written information about the trial in a form that the subject can read and understand. This form (see Appendix 10: Patient information sheet - Informed Consent Form) aims at detailing study purpose and methods, background and present knowledge of investigational product, benefits, risks, study assessments including full exams performed, personal data access and treatment, subject's right regarding the possibility, at any time, to withdraw his/her consent for participating in the study, without penalty about treatment he would beneficiate afterwards. Subject must be given sufficient time and opportunity to inquire about details, discuss and decide on his/her participation with the investigator concerned.

A voluntary, signed and dated Informed Consent Form must be obtained from the subject before any specific study screening procedure. Alternatively, the consent can be given orally in the presence of an independent witness who will sign the Informed Consent Form. Healthy subjects must always give signed informed consent. The written informed consent must be signed and dated by the person who conducted the informed consent procedure. The original will be filed in Investigator Study File; a copy of the document will be retained by the subject and another one will be collected by the sponsor (Assurance Quality Department) in secured sleeves.

If information becomes available that may be relevant to the subject's willingness to continue participating in the trial, the Investigator must inform the subject in a timely manner, and a revised written informed consent must be obtained.

16.3 Source data

Source data mean data the patient medical file contains, including but not limited to: medical history, concomitant medication (received or withdrawn), clinical assessment, vital signs, any original document such as exam reports, laboratory results, consultant letters and correspondence, nurse's notes...

NB: patient's involvement in the study should be clearly documented in his/her medical file; details should include the study protocol number, the hospital/unit code, the patient's identification and randomization number, the patient's consent to take part in the study (with the date of consent), the dates of all study visits.

Such essential documents must be retained by the investigator in accordance with local regulations (see section 20).

Any or part of data source may be recorded in the CRF (see section 12) for study purpose.

16.4 Access to source data

By signing Informed consent Form, the subject agrees that investigators, monitors and all mandated staff have access to his/her personal data to ensure control and quality of data recorded for corresponding study purposes only.

By agreeing to participate in this clinical trial, the investigator agrees to give full and direct access to sponsor, or mandated staff or health authorities to source data for each patient enrolled, in the course of trial related monitoring, audits, IRB/IEC review and regulatory inspection.

Subject may accede to his/her personal data on written request, for information or corrective purpose.

16.5 Source data confidentiality

Investigators and any study team member who have patient data access are subject to professional secrecy.

Source data recorded will be treated on an anonymous way. For this purpose, complete patient first name and last name will not appear in any study record. Data will be related to subject identified by a single number (see section 7.3 for assignment to subject number).

In countries where it is authorized by local regulations, patients may also be identified with initials (first two letters from last name followed by first letter from first name).

In accordance with legal requirements, anyone having direct access to source data must respect data confidentiality and follow any specific procedure to warrant subject anonymity on documents that could be forwarded to the sponsor.

16.6 Source data electronic management

Data from subjects enrolled will be encrypted so as to warrant subject anonymity, in accordance with laws regarding electronic data treatment.

17. Duration and termination of trial

17.1 Trial duration

Trial assessment will last 24 months for each patient.

Patient treatment will consist in successive 28-days blocks of low intensive chemotherapy (number of blocks depends on treatment response).

Investigational product is given/ provided during the whole period the patient is under low intensive chemotherapy.

Recruitment period planed: 3 years

Expected start date: Q1 2013

Expected completion date: Q1 2018

